#### **8.10.5. Inflammation Biomarkers**

Markers of inflammation include hs-CRP, IL-6, ICAM-1, and VCAM-1, which will be analyzed in the same manner as specified in [Section 8.10.4](#).

### **8.10.6. Proteinuria Biomarkers**

Proteinuria biomarkers include estimated glomerular filtration rate (eGFR), urine protein including urine protein-to-creatinine ratio (UPCR), and urine albumin-to-creatinine ratio (UACR), which will be analyzed in the same manner as specified in [Section 8.10.4](#).

### **8.10.7. Anthropometric Measures**

Anthropometric measures include body weight (kg) and BMI ( $\text{kg}/\text{m}^2$ ). BMI will be programmatically calculated for every visit where there is a weight collected, using the screening height. Weight will be analyzed in the same manner as specified in [Section 8.10.4](#).

Percent change in weight will be categorized as follows:

- At Least 5% Decrease
- All Other Patients (minor decrease [up to 5%], stable, or increase)

The number and percentage, with associated two-sided exact (Clopper-Pearson) 90 and 95% CIs, of patients in each category will be presented by treatment group. P-values from a Chi-square test will be presented for each pairwise comparison.

### **8.10.8. Dose Response**

Dose-response analyses for ALT, AST, GGT, cT1, MRI-PDFF, CK-18 (M30 and M65), PRO-C3, C3M, and PROro-C3/C3M ratio will be performed using the same methodology specified in [Section 8.8.4.4](#).

## **9. SAFETY ANALYSES**

Safety analyses will be conducted using the Safety Analysis Set.

No inferential comparison of safety endpoints will be performed, unless otherwise specified.

### **9.1. Extent of Exposure**

Total duration of exposure will be calculated in days as the last date study drug administration – the first date study drug administration + 1. In addition, duration of exposure accounting for days where a dose was missed (referred to as interruptions on CRFs) will be calculated as (last date study drug administration – the first date study drug administration + 1) – sum of (Week X date of resumption – Week X start date of interruption) where X is the week number, i.e., 2, 4, 6, 8, and 12. The dates of interruption are from the Study Drug Interruptions CRF. If dates of missed doses are not available, the number of missed doses will be used. Duration of exposure, total and accounting for missed dosing days, will be summarized with descriptive statistics by treatment group.

The number and percentage of patients with any missed dose and the total duration of days where doses were missed will be summarized with descriptive statistics by treatment group.

Treatment compliance will be calculated based on the Study Drug Administration and Study Drug Interruptions CRFs and separately based on the Study Drug Accountability CRF.

Compliance based on the Study Drug Administration and Study Drug Interruptions CRFs will be calculated as:

- $100 \times [((\text{last date study drug administration} - \text{the first date study drug administration} + 1) - \text{sum of missed dose durations}) / (\text{last date study drug administration} - \text{the first date study drug administration} + 1)]$ .

Compliance based on study drug accountability will be calculated as:

- $100 \times [(\text{Sum of capsules taken during study}) / (\text{Expected Taken})]$

For Part 2, capsules will be summed across the 2 bottles at each week.

For subjects in Part 1, expected taken is calculated as the study day of the last dose date. For subjects in Part 2, expected taken is calculated as the study day of the last dose date  $\times 2$ . Each treatment compliance will be summarized with descriptive statistics by treatment group. Number and percent of patients in each of the following compliance categories will be summarized by treatment group and overall total:

- <80%
- 80% to  $\leq 100\%$
- $>100\%$ .

Study drug administration including missed doses, delays, and overdoses, and study drug dispensing and accountability, calculated durations of exposure, and calculated compliances will be presented in by-patient data listings. Compliance with fasting conditions will be presented in a separate by-patient data listings.

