6.1. Study Drug(s) Administered

Investigational Medicinal Product	TERN-201 capsules	Placebo-to-match (identical in shape, size, appearance, and color to TERN-201 capsules)
Type	Drug	Drug
Dose Formulation	Capsule	Capsule
Unit Dose Strength(s)	1, 3, or 10 mg per capsule	Matching placebo per capsule
Route of Administration	Oral	Oral
Use	Experimental	Placebo
IMP/NIMP	IMP	IMP
Sourcing	Provided centrally by the Sponsor	Provided centrally by the Sponsor
Packaging and Labeling	Study drug will be provided in a labeled carton that contains HDPE bottle(s). In Part 1, each carton will contain one bottle for 4-week usage. In Part 2, each carton will contain two bottles for 4-week usage. Each bottle will be labeled as required per country requirements.	Study drug will be provided in a labeled carton that contains HDPE bottle(s). In Part 1, each carton will contain one bottle for 4-week usage. In Part 2, each carton will contain two bottles for 4-week usage. Each bottle will be labeled as required per country requirements.

Abbreviations: HDPE = High-density polyethylene; IMP = investigational medicinal product; NIMP = non investigational medicinal product

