6.2. Study Drug Administration

Patients will be instructed to take capsules as shown in [Table 1](#).

Table 1 Study Drug by Dose Group

Dose Group	TERN-201 Capsules	Placebo-to-Match
Part 1 – 10 mg	One 10-mg capsule QD	One placebo capsule QD
Part 2 – 4 mg	One 1-mg capsule and one 3 mg capsule QD	Two placebo capsules QD
Part 2 – 20 mg	Two 10-mg capsules QD	Two placebo capsules QD

Abbreviations: QD = once per day

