**Table 2: Study Administration by Dose Group**

Dose Group	TERN-201 Capsules	Placebo-to-Match
Part 1 – 10 mg	One 10 mg capsule QD	One placebo capsule QD
Part 2 – 4 mg	One 1 mg capsule and one 3 mg capsule QD	Two placebo capsules QD
Part 2 – 20 mg	Two 10 mg capsules QD	Two placebo capsules QD

**Abbreviations:** QD = once per day

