**Table 5: Analysis Sets**

Analysis Sets	Description
Screened	All patients who sign the informed consent form (ICF).
Randomized	All patients randomized into any one of treatment groups. Treatment assignment will be based on the randomized treatment.
Pharmacokinetic (PK)	All randomized patients who received at least 1 dose of TERN-201 and have evaluable PK data. Evaluable PK data is defined in Section 8.7 .
Pharmacodynamic (PD)	All randomized patients who received at least 1 dose of study drug (TERN-201 or placebo) and for whom at least one post baseline assessment of VAP-1/SSAO activity and methylamine is available. Treatment assignment will be based on the treatment actually received.
PK/PD Substudy	All patients who consented to the PK/PD substudy, were randomized into the PK/PD substudy, and received at least 1 dose of study drug (TERN-201 or placebo). Treatment assignment will be based on the treatment actually received.
Safety	All patients who received at least 1 dose of study drug. Treatment assignment will be based on the treatment actually received.
Efficacy	All randomized patients who received at least 1 dose of study drug. Treatment assignment will be based on the randomized treatment.
Per Protocol (PP)	All randomized patients who have completed the study without any major protocol deviations. Treatment assignment will be based on the treatment actually received.
Treatment Completer	All patients who complete 12 weeks of treatment with at least 80% compliance based on study drug accountability. Treatment assignment will be based on the randomized treatment.

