## **8.10. Exploratory Efficacy Analyses**

### **8.10.1. Magnetic Resonance Imaging**

MRIs will be evaluated by a central reader. The following analyses of MRI will use the Efficacy Analysis Set. Sensitivity analyses using the PP and Treatment Completer Analysis Sets will be presented if the analysis set differs from the Efficacy Analysis Set by more than 10% total.

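### SAP 9.1 counts 1 mg and 3 mg capsules alike, so in the 4 mg arm 80% capsule compliance can mean 70% to 90% of the assigned dose, and Treatment Completer membership can be wrong in either direction

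*SAP*

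**What the plan says.** The SAP gives the 4 mg regimen as "One 1 mg capsule and one 3 mg capsule QD" and the 20 mg regimen as "Two 10 mg capsules QD" (Table 2). Protocol 6.2 has the same 4 mg regimen. On packaging, Protocol 6.1 states: "In Part 2, each carton will contain two bottles for 4-week usage". Neither document says that each bottle holds a single strength.

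SAP 9.1 defines accountability compliance as 100 times capsules taken over capsules expected. For the numerator: "For Part 2, capsules will be summed across the 2 bottles at each week". For the denominator: "For subjects in Part 2, expected taken is calculated as the study day of the last dose date", multiplied by 2. There is no weighting by strength and no rule for each bottle. The result is reported as below 80%, 80% to 100%, and above 100%.

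SAP Table 5 then defines the Treatment Completer set as "All patients who complete 12 weeks of treatment with at least 80% compliance based on study drug accountability", with no upper limit. The set is used in the baseline tables (SAP 7.2) and in sensitivity analyses of the imaging, elastography, liver test and biomarker endpoints (SAP 8.10). Those are conditional: they appear only where membership departs from the Efficacy set by over 10% (SAP 8.10.1).

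**The concern.** Where the two daily capsules have equal strength, a capsule count is a dose count. In the 4 mg arm they do not, and a missed 3 mg capsule costs three times the dose of a missed 1 mg capsule while both lower compliance equally. The same percentage then means different things in arms shown side by side.

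Two things are at stake. The compliance table is where a reader would look to judge whether a weak 4 mg result reflects the dose or the dosing. And the 80% cut for the Treatment Completer set rests on this measure alone.

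Nothing else in the SAP repairs it. The second compliance measure in SAP 9.1 counts days, does not use strength and does not define the set. Accountability is listed by patient, but no rule uses the listing to correct membership. Receiving the wrong treatment or being dispensed an incorrect dose is a major deviation (SAP 7.3), which affects the Per Protocol set and not Treatment Completer.

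**Working it through.** **Inputs.** 4 mg arm: one 1 mg and one 3 mg capsule per day (SAP Table 2). Expected capsules: 2 × study day of last dose (SAP 9.1). Cut: at least 80% (SAP Table 5). Last dose on Day 85, the Week 12 target day. Assumption: one strength per bottle.

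**The plan's own figure.** Expected capsules are 2 × 85 = 170, so the cut is 0.80 × 170 = 136. Assigned dose is 85 × 4 = 340 mg.

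**Formulas.** Let f1 and f3 be the fractions of expected 1 mg and 3 mg capsules taken.

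- Capsule compliance (SAP): C = (f1 + f3)/2
- Dose compliance: M = (f1 + 3·f3)/4
- Difference: M − C = (f3 − f1)/4

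The two agree only when f1 = f3, that is, when the bottles are used equally. In the 20 mg arm M = (10·fa + 10·fb)/20 = (fa + fb)/2 = C for any pattern of use.

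**Cases at Day 85, neither bottle over-used.**

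| 1 mg taken | 3 mg taken | Capsules | mg | Result under the SAP |
|---|---|---|---|---|
| 85 | 51 | 136/170 = 80.0% | (85 + 153)/340 = 238/340 = 70.0% | included |
| 51 | 85 | 136/170 = 80.0% | (51 + 255)/340 = 306/340 = 90.0% | included |
| 50 | 85 | 135/170 = 79.4% | (50 + 255)/340 = 305/340 = 89.7% | excluded |

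Enumerating all counts from 0 to 85 per bottle, 70.0% is the lowest dose that passes the cut and 89.7% the highest that fails it.

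**If bottles hold spare capsules.** Capsules per bottle are not stated. Assuming 28, 30, 32 or 35 per 28-day bottle, the lowest dose compliance at exactly 80% by capsules is 70.0%, 66.4%, 62.9% or 57.5%.

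**Emptying the bottles in turn.** Assume 28 per bottle and two capsules a day from one bottle, then from the other. The carton supplies 14 × 2 mg + 14 × 6 mg = 112 mg, which equals 28 × 4 mg. Total dose and capsule compliance are both 100%, although the dose is 2 mg or 6 mg each day. With dispensing at Weeks 0, 4 and 8, the Week 2 and Week 6 samples would each follow about 14 days at 2 mg or 6 mg.

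**The case against.** The strongest case against acting is that the failure is narrow and the consequence small. To pass at 70% of dose, a patient must skip 34 of 85 of the 3 mg capsules while taking every 1 mg capsule. Patients who take or miss both capsules together are measured correctly, and one who never opens one bottle scores 50% and is caught. Part 2 is conditional, and the 4 mg arm is optional within it, with about 20 patients. The Treatment Completer set supports only baseline tables and conditional sensitivity analyses, and SAP 8.6 treats all testing as nominal. All of this stands and limits the size of the point. It does not make the rule measure dose.

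A reader might also infer more than the documents support:

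- **That taking two capsules from one bottle gives 50% or 150% of dose at 100% compliance.** This is true of single days, but it cannot outlast one bottle's supply. Once both bottles are emptied, the total is the assigned mg.
- **That such mix-ups are likely because the bottles look alike.** The documents say that placebo capsules match the active capsules and that bottles are labelled. They do not describe how the bottles look.
- **That the dose-response results are distorted through this measure.** The models use assigned group as a factor (SAP 8.8.4.4 and 8.10.8), and exposure-response uses measured PK (SAP 8.9). Compliance enters neither.
- **That overdosing goes unseen.** Regimen deviations and doses above the protocol dose are to be recorded (Protocol 6.5 and 8.6), and overdoses are listed (SAP 9.1 and Section 10). These depend on detection, but the above-100% category is not the only safeguard.

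**Conclusion.** The point holds as a correction to one rule. In the 4 mg arm the SAP's compliance figure can differ from dose compliance by a quarter of the difference in bottle use. With no over-use, 80% by capsules at Day 85 spans 70% to 90% of assigned mg. Patients can be misclassified in both directions: included at 70.0%, or excluded at 89.7%. The documents do not show how often this would happen, so the claim is that under-dosed patients can pass, not that they will.

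The conclusion rests on one strength per bottle, which follows naturally from two bottles per carton and the regimen but is not stated. The figures below 70% rest further on assumed spare capsules. The effect is confined to the 4 mg arm's compliance table and to analyses on the Treatment Completer set. Primary safety, Efficacy-set and dose-response-by-group analyses do not change.

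**What to change.** In SAP 9.1, define accountability compliance as mg taken divided by mg assigned, with capsules weighted by strength. Use it for the compliance categories and for the 80% Treatment Completer cut. Part 1 and the tabulated 20 mg regimen are numerically unchanged; for placebo, keep the capsule count. Since SAP 9.1 already sums over the two bottles at each week, the counts by bottle should exist.

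In addition, list counts by bottle at each accountability visit and flag any bottle in the 4 mg arm used faster than one capsule per day. Whole-study totals, by capsule or by mg, would not reveal sequential use of the bottles.

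Do not require 80% in the lower of the two bottles instead. A patient taking 67 of 85 of the 1 mg capsules (78.8%) and all of the 3 mg capsules would be excluded at (67 + 255)/340 = 322/340 = 94.7% of dose, whereas the present rule scores 152/170 = 89.4% and keeps the patient. In the 20 mg arm uneven bottle use is no dose error at all.

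Cost: SAP wording and a little programming. Bottle strength has to be linked after unblinding, so the rule must be fixed beforehand. Treatment Completer membership may change slightly.

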## 9.2. Adverse Events

Adverse event (AE) verbatim terms on eCRFs will be mapped to preferred terms (PT) and system organ classes (SOC) using MedDRA. AE severity will be categorized using the National Cancer Institute Common Terminology Criteria for Adverse Events (NCI CTCAE, Version 5).

All AEs will be listed, but summaries will be restricted to TEAEs, defined as any AE with a start date on or after the date of first administration of study drug through 30 days after the last administration of study drug or through the Follow-Up Period (Week 16). Related SAEs after Week 16 will be considered TEAEs. If it cannot be determined whether an AE is treatment emergent due to a partial onset date, then it will be counted as such. Methodology for imputation of partial AE start and stop dates is described in [Appendix 2](#). Each summary will be displayed by treatment group.

### 9.2.1. Overall Summary of Adverse Events

An overall summary of TEAEs will be presented by treatment group. The number and percentage of patients who experience at least one of the following:

- Any TEAE, All CTCAE grades
- TEAE by Maximum Severity
- Serious TEAE

- TEAE leading to death
- Treatment-related TEAE, All CTCAE grades
- Treatment-related Grade 3 or higher TEAE
- Treatment-related serious TEAE
- TEAE leading to study drug interruption
- TEAE leading to study drug discontinued
- TEAE leading to discontinuation from the study

### **9.2.2. Patient Incidence of Adverse Events**

Summaries will be displayed by SOC and PT, and will be ordered by descending order of all TERN-201 incidence of system organ class and preferred term within each system organ class. Summaries of the following types will be presented:

- Patient incidence of TEAEs by MedDRA SOC and PT.
- Patient incidence of non-COVID TEAEs for patients who have a TEAE of COVID-19.
- Patient incidence of TEAEs by MedDRA SOC, PT, and highest severity (CTCAE grade). At each level of patient summarization, a patient is classified according to the highest severity if the patient reported 1 or more events. AEs with missing severity (CTCAE grade) will be considered Grade 3 (severe) for this summary.
- Patient incidence of CTCAE Grade 3 or higher TEAEs by MedDRA SOC and PT. At each level of patient summarization, a patient is classified according to the highest severity if the patient reported 1 or more events. AEs with missing severity (CTCAE grade) will be considered Grade 3 (severe) for this summary.
- Patient incidence of treatment-related TEAEs by MedDRA SOC and PT. Related AEs are those with relationships reported as “Related” or “Possibly Related”. At each level of patient summarization, a patient is classified according to the closest relationship to study drug if the patient reported 1 or more events. AEs with a missing relationship will be considered related for this summary.
- Patient incidence of treatment-related CTCAE Grade 3 or higher TEAEs by MedDRA SOC and PT. At each level of patient summarization, a patient is classified according to the highest severity if the patient reported 1 or more events. AEs with missing severity (CTCAE grade) will be considered Grade 3 (severe) for this summary. AEs with a missing relationship will be considered related for this summary.
- Patient incidence of serious TEAEs by MedDRA SOC and PT.
- Patient incidence of TEAEs leading to study drug discontinued by MedDRA SOC and PT. This is a subset of the AEs where Action Taken with Study Drug is checked as “Drug Withdrawn.”

The following listings will be presented by treatment group and patient, include study day event started and the duration of event:

- All adverse events.
- Serious adverse events (subset of the AEs where serious is marked as “Yes”).
- CTCAE Grade 3 or higher adverse events (subset of AEs where severity is marked as CTCAE Grade 3, 4, or 5).
- Related adverse events (subset of the AEs where relationship marked as “Related” or “Possibly Related”).
- Adverse events leading to study drug interruption (subset of the AEs where Action Taken with Study Drug is checked as “Study drug interrupted”).
- Adverse events leading to study drug discontinued (subset of the AEs where Action Taken with Study Drug is checked as “Drug Withdrawn”).
- Adverse events leading to death (subset of the AEs where outcome is indicated as “Fatal” or the CTCAE grade is 5 or seriousness criteria is Death).

### **9.3. Clinical Safety Laboratory Evaluations**

All laboratory assessments are specified in Appendix 1 of the study protocol. Laboratory parameters will be summarized in conventional units. Coagulation parameters, hemoglobin A1c, direct bilirubin, and indirect bilirubin will not be summarized.

Quantitative serum chemistry, fasting lipids, and hematology results will be summarized by treatment group using descriptive statistics at baseline and at each post-baseline visit. The change and percent change from baseline will also be summarized.

Values determined to be erroneous will be documented in the trial master file and analysis data reviewer’s guide. Erroneous values will not be included in summary tables or analyses but will be included in patient listings.

All clinical safety laboratory data will be presented in by-patient data listings. A separate listing for central laboratory normal ranges, by lab category, lab test, lab parameter, sex, and age, will be presented. Any local laboratory normal ranges for COVID-19 will be presented separately.

#### **9.3.1. Treatment Emergent Abnormalities**

Quantitative laboratory tests will be assigned grades based on National Cancer Institute Common Terminology Criteria for Adverse Events (NCI CTCAE) Version 5. For each applicable laboratory test, a treatment emergent abnormality will be defined as a post-baseline through Week 16 CTCAE grade worsening of  $\geq 2$  grades.

The number and percentage of patients overall and by laboratory test, with any treatment emergent laboratory abnormality, CTCAE worsening of  $\geq 2$  grades, will be presented.

Listings will be presented for any patient with any treatment emergent laboratory abnormality (any increase in CTCAE grade). Normal ranges provided by the central laboratory will be presented in a listing.

### 9.3.2. Assessments of Potential Drug Induced Liver Injury

Modified Hy's rule by Bjornsson ([Bjornsson 2005](#)) is defined as patients with ALT or AST values  $>3$  ULN and total bilirubin  $>2$  ULN (based on the same blood draw of ALT, AST, and total bilirubin while on study drug, or within 30 days of last received dose) will be used to assess the potential for study drug-induced liver toxicity. Any patient meeting the criteria will be presented in a by-patient listing.

The criteria for increased laboratory monitoring or consideration for study drug discontinuation on study are specified in protocol appendix 3 and will be included in the analysis dataset and listed.

